8.3 Follow-up

Study Day 7

Allowable window for clinic visit is 7±3 days from Study Day 0 visit date.

- 1. Verbally reconfirm consent.
- 2. Update medical history including use of medications.
- 3. Screening for potential new TB exposure and TB symptoms.
- 4. Record feeding practice.
- 5. Vital signs (heart rate, respiratory rate, axillary temperature, weight and recumbent length).
- 6. Focused physical examination.
- 7. Collect and review solicited AE and medication diary card entries for completeness and accuracy. Redistribute AE and medication diary card.
- 8. Record any adverse events, including systemic solicited adverse events, unsolicited adverse events, solicited and unsolicited injection site reactions, and serious adverse events (including concomitant medications).
- 9. Examine site of injection (includes measurement of redness, swelling, and ulceration) and take a pus swab if discharge present.

10. Blood collection for:

- Serum chemistry: includes AST, ALT, GGT, total bilirubin, creatinine.
- Hematology: includes full blood count with differential, and platelet count.

Study Day 28

Allowable window for clinic visit is 28±3 days from Study Day 0 visit date.

- 1. Verbally reconfirm consent.
- 2. Update medical history including use of medications.
- 3. Screening for potential new TB exposure and TB symptoms.
- 4. Record feeding practice.
- 5. Vital signs (heart rate, respiratory rate, axillary temperature, weight and recumbent length).
- 6. Focused physical examination.
- 7. Collect and review solicited AE and medication diary card entries for completeness and accuracy.
- 8. Record any adverse events, including systemic solicited adverse events, unsolicited adverse events, solicited and unsolicited injection site reactions, and serious adverse events (including concomitant medications).
- 9. Examine site of injection (includes measurement of redness, swelling, and ulceration) and take a pus swab if discharge present.
- 10. Blood collection for:
 - Immunogenicity WB-ICS

Study Day 56

Allowable window for clinic visit is 56±7 days from Study Day 0 visit date.

- 1. Verbally reconfirm consent.
- 2. Update medical history including use of medications.
- 3. Screening for potential new TB exposure and TB symptoms.
- 4. Record feeding practice.
- 5. Vital signs (heart rate, respiratory rate, axillary temperature, weight and recumbent length).
- 6. Focused physical examination.

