9 STUDY PROCEDURES/EVALUATIONS

9.1 Clinical Evaluations

Participants will have vital signs taken prior to study vaccination. Participants will remain in the clinic under close observation for at least 60 minutes after receiving investigational product. Vital signs will be repeated at 60±10 minutes post-vaccination before participants leave the clinic. Allergic reactions to vaccination are possible; therefore, appropriate paediatric drugs and medical equipment to treat acute paediatric anaphylactic reactions must be immediately available, and a medically qualified study team member trained to recognize and treat anaphylaxis must be present in the clinic during the entire vaccination procedure and post-vaccination monitoring period.

Clinical assessments to be performed at each visit are summarized in Appendix A and listed by visit in Section 8.

Participants' caregivers will receive, and be instructed in, the operation of a daily adverse event diary, ruler (for measurement of redness, swelling, and ulceration), and a digital thermometer to measure axillary temperature, to be used during the 7 days post-vaccination diary period after investigational product administration. The daily adverse event diary is a tool to help aid the principal investigator or designee to engage in a conversation with the participant's caregiver about any AEs that may have occurred between visits. During scheduled visits through the specified diary period and after investigational product administration, the daily diary will be collected and reviewed by the principal investigator or designee at which time any clinical details required for complete understanding of the information recorded will be obtained. If possible, diaries not brought to the scheduled visit should be obtained before adverse event assessment can be performed and events discussed with the principal investigator or designee. If a diary is lost, the principal investigator or designee will discuss the occurrence of any solicited adverse events with the participant's caregiver and document the discussion. Information on the diary card will not be directly recorded onto eCRFs. The diary card will be considered source documentation and adverse event information obtained from the diary card will be recorded and completely assessed on the adverse event eCRF. Axillary temperatures below 38°C will not be considered fevers.

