The reporting period for all adverse events is specified in Section 10.1. Adverse events will be reported using a recognized medical term or diagnosis that accurately reflects the event. Adverse event evaluations will be reviewed by the principal investigator or sub-investigator. AE information is to be completed by members of the study team designated in writing by the principal investigator. The onset and resolution dates of the event and action taken in response to the event will be documented.

Assessing Severity

The safety concepts of "severity" and "seriousness" are distinct concepts (see Section 10.2.3). "Severity" refers to a degree of clinical manifestation. "Seriousness" refers to defined outcomes from an adverse event. A severe adverse event is not always serious, and a serious adverse event is not always severe.

For all adverse events, the investigator is responsible for assessing the severity of the event and the causal relationship of the event to the investigational product.

The severity of all adverse events, including clinical findings and abnormal laboratory values, will be classified as one of the following grades:

- 1. Mild
- 2. Moderate
- 3. Severe

Toxicity Tables are provided in the protocol appendices for the assessment of severity of specified adverse events. The Toxicity Table Adverse Event Grades do not correlate directly with the classical severity grades of mild, moderate and severe. FOR THE PURPOSES OF RECORDING EVENTS ON THE eCRF, Toxicity Table Grade 1 events will be considered mild in severity, Toxicity Table Grade 2 events will be considered moderate in severity, and both Toxicity Table Grade 3 and 4 events will be considered as severe.

For adverse events not listed in the Toxicity Table determination of severity requires some level of interpretation as outlined below. The degree of incapacity caused by the adverse event and the level of medical intervention required for treatment may be helpful in assessing the overall severity of the adverse event.

For example:

- "Mild" events are generally regarded as noticeable but have no impact on normal activities; they may or may not require over-the-counter treatment managed by the participant's caregiver.
- "Moderate" events generally have some impact on an individual's normal activities and may require general symptomatic medical intervention by a healthcare professional or by the participant's caregiver.

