- "Severe" adverse events may be incapacitating, leading to suspension of normal daily activities, and would generally require more immediate medical evaluation and intervention by a healthcare professional.

A change in severity of an adverse event will not be recorded as a new adverse event. Only the highest severity level that occurs during the entire period of the adverse event will be recorded on the eCRF with the onset and resolution dates encompassing the entire duration of the event.

Assessing Causal Relationship (Relatedness)

For all adverse events, the investigator and, for SAEs, the sponsor and local medical monitor, will determine a **causal relationship** to the investigational product without knowledge, for blinded studies, of whether active vaccine or active control was administered. A number of factors will be considered in making this assessment, including: 1) the temporal relationship of the event to the administration of the investigational product 2) whether an alternative etiology has been identified, and 3) biological plausibility.

The investigator will use the following guidelines to assess the causal relationship of an adverse event to study vaccine:

- Not Related to study vaccine (i.e., there is no evidence of a causal relationship; another
 etiology is known to have caused the adverse event. The alternative etiology should be
 documented in the participant's study record).
- **Unlikely Related** to study vaccine (i.e., there is less than a reasonable possibility that the adverse event was caused by study vaccine).
- Possible relationship to study vaccine (i.e., there is a reasonable possibility that the
 adverse event was caused by study vaccine. There must be a plausible mechanism for
 the event to be related to study vaccine. The evidence is inadequate to accept or reject,
 or favours rejection of, a causal relationship; an association exists between the event and
 the study vaccine but there may also be an alternative etiology, such as characteristics of
 the participant's clinical status or underlying condition).
- Probable relationship to study vaccine (i.e., it is likely that the adverse event was caused
 by administration of the study vaccine. The evidence favours acceptance of a causal
 relationship; an association exists between the event and receipt of the study vaccine and
 there is a plausible mechanism for the event to be related to the study vaccine, and an
 alternative etiology is not apparent).

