12.4.4 Safety Analyses

12.4.4.1 Adverse Events

The primary endpoint is the frequency of adverse events (AEs) by MTBVAC dose compared to BCG. In order to assess the primary endpoint, analysis of the data will be preceded by a

blinded data review meeting in order to address population determination and miscellaneous data queries pertinent to analysis of the primary endpoint.

Safety and reactogenicity data will be evaluated by study arm and cohort in all participants in the safety analysis set. The primary variable for evaluation of safety will be the frequency of unsolicited, solicited adverse events and injection site reactions at all available post-vaccination time points. The number and percentage of participants with adverse events will be summarized by MedDRA system organ class (SOC) and preferred term (PT), as well as by severity and relationship to study vaccine. Informal between-group comparisons will be performed using the Chi-square or Fisher Exact test. The Cochran-Mantel-Haenzel test will be used to compare the effect of dose on reactogenicity (injection site adverse events).

Separate listings will be provided for participants with serious adverse events. SAEs may also be summarized by MedDRA system organ class and preferred term.

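### The planned reactogenicity comparison with BCG commits no test to the order of the severity grades and leaves the measured reaction diameters unused

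*Combined protocol and SAP*

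**What the plan says.** Reactogenicity of escalating MTBVAC doses compared with BCG is part of the first primary objective (Section 4.1). Section 12.4.4.1 sets the outcome: "The primary variable for evaluation of safety will be the frequency of unsolicited, solicited adverse events and injection site reactions", over all available time points after vaccination. Results are summarised as the number and percentage of participants with events, with breakdowns by severity and relationship. Two tests are named:

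- Between groups: "Informal between-group comparisons will be performed using the Chi-square or Fisher Exact test".
- Across doses: "The Cochran-Mantel-Haenzel test will be used to compare the effect of dose on reactogenicity (injection site adverse events"). No CMH statistic, scores or strata are given, and the place of BCG in the test is not stated.

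The data collected are richer. At Days 7, 28, 56 and 182 the instruction is: "Examine site of injection (includes measurement of redness, swelling, and ulceration) and take a pus swab if discharge present". Sections 8.2 and 8.4 require the same measurements on Day 0 and Day 365. Appendix B grades erythema, induration and ulceration by maximum diameter in mm, with Grade 1 starting above 2 mm, and gives ordered grades for tenderness and regional lymphadenopathy.

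For the eCRF, Section 10.2.1 says "Only the highest severity level that occurs during the entire period of the adverse event will be recorded on the eCRF", and that "both Toxicity Table Grade 3 and 4 events will be considered as severe".

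Section 12.4.4.2 plans continuous summaries for laboratory and vital-sign values, and Section 12.4.3 plans means, medians and mixed models for immunology. Nothing in Section 12 does either for the injection-site diameters.

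**The concern.** Every arm receives a live intradermal mycobacterial vaccine, and a reaction of just over 2 mm already counts as Grade 1. It is therefore plausible, though the documents do not say so, that most infants in every arm will have some local reaction. The proportion with any reaction is then close to its ceiling in all arms, and differences between doses lie in size and grade. A comparison of counts would say little about them.

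This comparison has a use. Section 12.3.1 bases the Phase III dose choice on all safety data available when Cohort 3 completes Day 182. An informative estimate of how local reactions grow with dose, relative to BCG, is one of the things the trial is placed to deliver.

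**Working it through.** **No figure in the plan to reproduce.** Sections 12.1 and 12.2 give no power, alpha or effect size. The allocation adds up: 3 × (25 + 8) = 75 + 24 = 99.

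**Inputs.** From the documents: 25 infants per MTBVAC dose, 24 BCG infants pooled over cohorts, and Grades 3 and 4 merged as on the eCRF. Assumed, because the documents give none: the BCG any-reaction rate (30% to 95%); a split of reactors of 65/28/7% over Grades 1/2/3+; a proportional odds ratio of 4 for a higher worst grade; two-sided 5%.

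**Model.** For each cut k, odds of grade ≥ k on MTBVAC = 4 × odds on BCG. At a 90% BCG rate:

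- Grade ≥ 1: 0.90/0.10 = 9; × 4 = 36; 36/37 = 0.973.
- Grade ≥ 2: 0.90 × 0.35 = 0.315; 0.315/0.685 = 0.460; × 4 = 1.839; probability 0.648.
- Grade ≥ 3: 0.90 × 0.07 = 0.063; 0.063/0.937 = 0.0672; × 4 = 0.269; probability 0.212.

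The any/none contrast is 90% v 97%, a gap of 7 points. The Grade ≥ 2 contrast is 31.5% v 64.8%, a gap of 33 points. At a 30% rate the any/none contrast is 30% v 63% (0.30/0.70 × 4 = 1.714; 1.714/2.714 = 0.632), so little is hidden.

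**Power, 25 v 24.** Ranges cover repeated simulations of 2,000 or more runs per cell; the simulation standard error near 70% is √(0.7 × 0.3/2000) ≈ 1 point.

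| Assumed BCG any-reaction rate | Fisher, any/none | Wilcoxon, worst grade |
|---|---|---|
| 30% | 63–64% | 68–70% |
| 50% | 55–57% | 72–73% |
| 70% | 40% | 71–73% |
| 80% | 26–27% | 71–73% |
| 90% | 5–6% | 70–72% |
| 95% | under 1% | 70–71% |

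Summing the two binomial distributions over all tables with Fisher p < 0.05 gives 63.5%, 39.5% and 5.3% at 30%, 70% and 90%, in line with the simulations. Wilcoxon type I error was 4 to 5%.

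**Other codings of the tests already named, at 90%.** Fisher on Grade ≥ 2: 63–65%. Chi-square on the full grade table: 50–51%. CMH row-mean-score on grade: 69–70%.

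**Different assumed shapes of effect.**

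- Severity-only shift, 95% reacting in both arms (none/G1/G2/G3/G4 of 5/70/20/5/0% v 5/35/45/14/1%): any/none 0.4%; graded tests 56–67%.
- Effect mainly on occurrence (50% v 85% reacting): any/none 72%; ordinal tests 69–74%; Fisher on Grade ≥ 2 only 26%.
- Dose trend over 25/25/25, severity only: any/none 3%; ordinal CMH correlation 59%.

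Neither fixed cut does well in both settings; the ordinal tests hold up in both.

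**Diameters.** Take an assumed median of 8 mm and log-SD of 0.4 to 0.6, with every infant above 0 mm. A 1.5-fold increase then stays largely within the Grade 1 band. Power is 94–66% on log mm, 19–30% on ordinal grade and 0% on any/none. This shows only that grading discards size information; it does not support a log-mm model, which fails for infants at 0 mm.

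**CMH strata.** If Cohort 3 receives the highest dose, each cohort contains a single MTBVAC dose. Within a cohort stratum, dose among MTBVAC recipients does not vary, so a dose test stratified by cohort has nothing to compare.

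**The case against.** The strongest reply is that Section 12.4.4.1 never says reactions are reduced to yes/no. Chi-square can be run on a grade table, Fisher on Grade ≥ 2, and CMH has ordinal forms. As shown above, those choices recover much or nearly all of the loss. This stands: the gap belongs to an any/none coding, which is the natural reading of a frequency but is not stated. The defect is therefore partly one of specification.

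A reader might go further and infer that a clear rise in severity with dose would go undetected, or that the trial would report no difference. The documents do not support that:

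- Sections 12.1 and 12.4.4.1 make the comparisons informal, so a p-value above 0.05 decides nothing.
- Events are tabulated by severity, the DSMB reviews all available safety data, and Section 10.5 lists severe or large injection-site reactions among the pausing triggers.

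Nor do the recording rules show that the data are lost. Section 9.1 says "Information on the diary card will not be directly recorded onto eCRFs", but goes on to say that event information from the card is assessed and recorded on the adverse event eCRF. Keeping the highest severity per event is what a worst-grade analysis needs. Section 16.4.2 has relevant source data transcribed, although no section specifically commits the visit-level mm values to the eCRF.

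Two further limits stand. Diameters are measured for redness, swelling and ulceration only, not for pain, drainage or lymphadenopathy. And a detailed SAP is still to be written before database lock (Section 12.4). It is the right place for these choices, but it can use only what has been captured.

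**Conclusion.** The point holds as a cheap improvement. Section 12.4.4.1 commits no test to the grade ordering, leaves the CMH test undefined, and plans no use of the diameters measured from Day 0 to Day 365. On the any/none reading, and under the assumed odds ratio of 4, the shortfall against an ordinal test is about 6 points of power at a 30% BCG reaction rate, about 30 at 70% and about 65 at 90%. It is negligible where dose mainly changes occurrence, and much smaller if the named tests are run on grades.

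All rates, grade splits and effect sizes are assumptions. The figures also use all 24 BCG infants. Against the 8 concurrent BCG infants of one cohort, even graded tests reach only 23–39% for the severity-only shift. The consequence is a less informative comparison on a primary objective, not a failed decision rule.

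**What to change.** In Section 12.4.4.1, and in the SAP when it is written:

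1. Make the reactogenicity comparison each infant's worst grade per local reaction, each MTBVAC dose against BCG, by Wilcoxon or CMH row-mean-score. Report a proportional odds ratio with 95% CI where it can be estimated, and state whether BCG is pooled or concurrent.
2. State that the CMH dose test is the ordinal correlation form across the ordered MTBVAC doses. Do not stratify it by cohort if Cohort 3 receives the highest dose, and acknowledge that dose and cohort then cannot be separated.
3. Summarise maximum diameter of redness, swelling and ulceration by visit and arm (median, IQR). Any comparison should be rank-based, because zeros rule out a log-mm model. Keep this descriptive: 3 reactions × 6 visits × 3 doses would be 54 comparisons.
4. Keep any/none counts as descriptive.
5. Confirm that the eCRF captures the visit-level mm values and the toxicity grade alongside mild/moderate/severe.

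Cost: some data entry for values already measured, and a few extra tables. No extra visits, procedures or infants.

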 To differentiate vaccine-induced immune responses from natural Mtb infection.

[figure not shown]
Design:

Double-blind, randomised, active BCG control, MTBVAC dose-finding trial with 3 cohorts of healthy, BCG naïve, HIV unexposed, South African newborns (24 BCG; 75 MTBVAC)

Estimated Time to Complete Enrollment:

The estimated time to complete enrollment is approximately 9 months.

Schematic of Study Design:

¹ Cohort 1: n=25 MTBVAC (2.5 x 104 CFU) and n=8 BCG

² Cohort 2: n=25 MTBVAC (2.5 x 10⁵ CFU) and n=8 BCG

³ Cohort 3: n=25 MTBVAC (2.5 x 106 CFU OR 2.5 x 105 CFU (n=13) plus 2.5 x 104 CFU (n=12)) and n=8 BCG

⁴ At each DSMB, all available safety data from previous cohorts enrolled will be reviewed. If any of the safety criteria is not met for the 2.5 x 10° CFU dose for Cohort 3, Cohorts 1 and 2 will be expanded so that 33 additional neonates will be randomly allocated to receive the 2.5 x 10° CFU dose (n=13), the 2.5 x 10° CFU dose (n=12) or BCG (n=8) by default.

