5 STUDY DESIGN

This double-blind, randomized, active controlled, MTBVAC dose-finding trial will evaluate the safety, reactogenicity, immunogenicity, and potential for QFT conversion and reversion of the candidate TB vaccine MTBVAC in HIV uninfected BCG naïve newborns, administered in 3 cohorts at a single intradermal dose of 2.5×10^4 CFU (Cohort 1, n=25), 2.5×10^5 CFU (Cohort 2, n=25), and either 2.5×10^6 CFU (n=25) or 2.5×10^5 CFU (n=13) plus 2.5×10^4 CFU (n=12) (Cohort 3), compared to BCG vaccine (24 BCG; 75 MTBVAC).

Three dose levels of MTBVAC (2.5 x 10³, 2.5 x 10⁴, 2.5 x 10⁵ CFU) have been tested in the current Phase 1b trial in healthy, BCG-naïve, South African newborns; and four dose levels (5 \times 10³, 5 x 10⁴, 5 x10⁵, and 5 x 10⁶ CFU) are being tested in a parallel trial among M. tuberculosis infected and uninfected South African adults. It is our hypothesis that the optimal safe and immunogenic MTBVAC dose for infants lies in the range of 2.5 x 104 (10-fold lower than BCG) to 2.5 x 10⁶ CFU (10-fold higher than BCG). Therefore, this proposed infant trial aims to define the MTBVAC dose-response curve above and below the optimal MTBVAC dose, straddling a 3-log dose range. Final selection of the MTBVAC dose for use in the 3rd cohort will be data driven, based upon the most recent safety and immunogenicity data from all ongoing and completed trials of MTBVAC in infants and adults at that time. Infant safety data are not yet available for the highest (2.5 x 10⁶ CFU) MTBVAC dose. Therefore, selection of the 2.5 x 106 CFU MTBVAC dose would be contingent upon demonstration of an acceptable safety profile (as defined in Section 3.3.1), both for all lower MTBVAC doses in infants, and for the 5 x 10⁶ CFU MTBVAC dose in QFT negative adults (data expected end 2018/beginning 2019). If these safety criteria for the highest MTBVAC dose are not fulfilled, the 2.5 x 10⁵ CFU and 2.5 x 104 CFU MTBVAC doses would be selected for the last cohort, as described in Section 3.3.1. This approach will build upon data from the current infant pilot study and should allow detailed comparison of safety and immunogenicity of the postulated optimal MTBVAC dose within a 3-log dose range, in a larger infant study population. Refer to Figure 5-1.

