12 STATISTICAL CONSIDERATIONS

12.1 Study Hypotheses

No formal hypothesis testing will be performed, since the trial is not powered to do any formal testing (see sample size section below).

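### No confidence interval is specified for any adverse event rate or MTBVAC-minus-BCG difference; the only between-group tools for the primary safety endpoint are informal p-value tests that say little at 25 v 24 infants

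*Combined protocol and SAP*

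**What the plan says.** Section 12.4.4.1 (Adverse Events) defines the endpoint: "The primary endpoint is the frequency of adverse events (AEs) by MTBVAC dose compared to BCG". The output is the number and percentage of participants with events by MedDRA class and term, severity and relationship. "Safety and reactogenicity data will be evaluated by study arm and cohort in all participants in the safety analysis set". On comparing groups: "Informal between-group comparisons will be performed using the Chi-square or Fisher Exact test". A CMH test is added for the effect of dose on injection-site events, and serious adverse events (SAEs) are listed separately.

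Section 12.1 says: "No formal hypothesis testing will be performed, since the trial is not powered to do any formal testing". Section 12.2 says that the 99 infants were not chosen on statistical grounds and that the aim is to pick up common events, major signals and important trends. Section 5 gives the split as "24 BCG; 75 MTBVAC": 25 MTBVAC and 8 BCG infants per cohort. Section 6.3.1 lists BCG as one group of 24.

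Section 12 names no confidence interval for AEs, no significance level, no rule for choosing between chi-square and Fisher, and no rule for interpreting a p-value. Section 12.4 calls itself an outline and defers detail to a separate statistical analysis plan, to be finalised before database lock and not included in the document reviewed.

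**The concern.** The endpoint is comparative. The only comparative statistic offered for it is of a kind that the plan itself calls underpowered. A p-value above 0.05 from two groups of about 25 can sit beside no excess or beside a substantial one. A bare percentage does not separate them either: 0% in 8 infants and 0% in 75 infants print alike.

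This matters because Section 3.2 describes going straight from this trial to Phase III with one selected dose. Sections 8.3 and 12.3.1 base that selection partly on these safety data, and Section 3.3.1 says that the safety of the highest dose in infants is not yet known. Readers need to see which excess over BCG the data have not ruled out. An interval shows that; a p-value does not.

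**Working it through.** **Inputs.** From Sections 5 and 6.3.1: 25 infants per MTBVAC dose and 24 pooled BCG (8 per cohort); 3×25 + 3×8 = 75 + 24 = 99, which agrees with the stated total. Assumed, because the plan gives none: two-sided 5% level, the event rates below, and no dropout. The plan states no power or detectable difference, so there is no such figure to reproduce.

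**1. Power of Fisher's test, 25 v 24.** Sum the binomial probabilities of all outcomes (x of 25, y of 24) with two-sided Fisher p≤0.05.

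| True MTBVAC v BCG rate | Power |
|---|---|
| 25% v 5% | 38% |
| 20% v 4% | 24% |
| 30% v 10% | 32% |
| 40% v 20% | 25% |
| 40% v 10% | 61% |

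The MTBVAC rate needed for 80% power is 30%, 39%, 48%, 60%, 70% or 88% when the BCG rate is 0%, 5%, 10%, 20%, 30% or 50%. That is an excess of 30 to 40 points. If the top dose is not used, the lower-dose arms become 25+12=37 and 25+13=38; power for 30% v 10% is then still only 38% to 40%.

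**2. What an interval adds.** Newcombe limits for d = p1−p2, with Wilson limits (l, u) for each arm: lower = d − √[(p1−l1)² + (u2−p2)²]; upper = d + √[(u1−p1)² + (p2−l2)²].

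For 6/25 v 1/24, d = 0.240 − 0.042 = 0.198, and the Wilson limits are (0.115, 0.434) and (0.007, 0.202).
- Lower: 0.198 − √(0.125² + 0.161²) = −0.005.
- Upper: 0.198 + √(0.194² + 0.034²) = 0.396.

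| Observed | Fisher p | Difference, points (95% CI) |
|---|---|---|
| 5/25 v 5/24 | 1.00 | −0.8 (−23.4 to 21.5) |
| 6/25 v 1/24 | 0.098 | 19.8 (−0.5 to 39.6) |
| 8/25 v 2/24 | 0.074 | 23.7 (0.7 to 44.2) |
| 5/25 v 0/24 | 0.0502 | 20.0 (2.3 to 39.1) |

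The first row is the plainest. A p-value of 1.00 looks like equality, yet an excess of about 21 points has not been ruled out.

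**3. No events seen.** The upper limit of the Clopper-Pearson 95% interval is 1 − 0.025^(1/n): 13.7% for 0/25, 14.2% for 0/24, 36.9% for 0/8 and 4.8% for 0/75.

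**4. The open choice of test.** For 8/25 v 2/24, uncorrected chi-square gives 0.040 and Fisher 0.074. The smallest expected count is 10×24/49 = 4.9, so the usual rule of five would narrowly favour Fisher. For 10/25 v 3/24 the smallest expected count is 13×24/49 = 6.4. The same rule would then allow chi-square, which gives 0.029 against Fisher's 0.051.

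**5. Within a cohort, 25 v 8, if tested at all.** Fisher power is 2% for 25% v 5% and 21% for 40% v 10%. The expected BCG count is 8 × the overall rate, so it is below 5 unless that rate exceeds 5/8 = 62.5%.

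**The case against.** The strongest reply is that nothing here rests on a p-value. The main output is counts and percentages, so a reader of 5/25 v 0/24 sees 20% v 0% whatever the test gives. The tests are labelled informal and formal testing is disclaimed. Safety decisions run through data safety monitoring board review and through pausing rules that do not use p-values (Sections 10.5, 10.7 and 12.3). The deferred analysis plan may add intervals. All of this stands, and it limits the point to reporting.

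A reader might infer that large excesses over BCG would be reported as no difference. The documents do not support that. No section states such a rule or sets a level, and at 25 v 24 excesses of 30 to 40 points have about 80% power over the BCG rates examined.

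A reader might also take the 25 v 8 figures as the planned comparison. Evaluation by arm and cohort does not clearly mean testing against 8 controls, so those figures are conditional.

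Finally, part of the contrast at 5/25 v 0/24 comes from setting a conservative exact test against a score-type interval. Fisher's p there is C(25,5)/C(49,5) + C(24,5)/C(49,5) = 0.0279 + 0.0223 = 0.0502. The case does not need that example: at 6/25 v 1/24 and 5/25 v 5/24 test and interval agree on significance, and the interval still says more.

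The informal label does not answer the remaining point. It does not make a non-significant p-value informative, and percentages alone do not show precision.

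**Conclusion.** The point holds as a gap in the analysis and reporting plan for the primary safety endpoint. Section 12.4.4.1 names only p-value tests for comparing groups and specifies no interval for any AE rate or difference. With 25 v 24 infants, true excesses of about 20 points would be non-significant by Fisher roughly 60% to 75% of the time (power 38% for 25% v 5%, 25% for 40% v 20%). Non-significance could therefore be misread as similar safety. Leaving chi-square or Fisher open adds an avoidable ambiguity near 0.05.

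The figures rest on an assumed two-sided 5% level, assumed event rates and no dropout. The absence of intervals is established for the document reviewed, not for the separate analysis plan. The change is worth making before that plan is finalised; the point does not show that the design or the safety oversight is unsound.

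**What to change.** In Section 12.4.4.1 and the analysis plan, for each solicited AE, any Grade 3 or higher AE, any related AE and any SAE:

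- Report each arm's percentage with a Clopper-Pearson 95% interval, including the upper limit when no event is seen.
- Make the risk difference, each MTBVAC dose minus pooled BCG, with a Newcombe or exact 95% interval, the main comparison. Name the interval method in advance.
- Keep Fisher, not chi-square, as a secondary descriptive test, and leave the CMH dose test for injection-site reactions in place.
- Present by-cohort results descriptively.
- State that p>0.05 will not be read as evidence of similar safety.

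The cost is wording and extra table columns, with no new data and no design change. The intervals will look wide and add no power; they make the existing imprecision visible.
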